
2. Overall Objectives - (Recruitment & Retention Pilot Study)

Aim 1: To evaluate the effects of information provision and incentives, alone and in combination, on study enrollment rates.

Hypothesis: Behavioral economic interventions will (Information provision & contingency management) will produce higher rates of enrollment compared to standard recruitment.

CHARACTERISTICS OF THE STUDY POPULATION

1. Target Population

400 healthy adult smokers between the ages of 18-65 will be enrolled in order to have 200 participants complete the study.

2. Accrual

400 male or female participants will be enrolled to have 200 complete the study at the University of Pennsylvania Center for Interdisciplinary Research on Nicotine Addiction (CIRNA). Accounting for ~50% attrition (primarily participants who are found to be ineligible during the intake session), we estimate we will need to enroll 400 eligible participants (~7 smokers per month over a 50 month period) to have up to 200 participants complete the study. Participants will first be screened over the telephone and then complete an in-person Intake Visit at the Center for Interdisciplinary Research on Nicotine Addictions to confirm final eligibility.

3. Key Inclusion Criteria

Eligible participants will be:

1. Smokers between the ages of 18 and 65, reporting consumption of at least 5 cigarettes per day for at least the past 6 months;
2. Planning to live in the area for at least the next 3 months;
3. Capable of giving written informed consent, which includes compliance with the requirements and restrictions listed in the combined consent and HIPAA form;
4. Able to communicate fluently in English (speaking, writing, and reading).

4. Key Exclusion Criteria

Subjects who present and/or self-report with the following criteria at any point during study participation will not be eligible to participate in the study:

Smoking Behavior:

1. Use of chewing tobacco or snuff or cigars;
2. Current enrollment or plans to enroll in another smoking cessation program or research study in the next 3 months;
3. Current or anticipated (within the next 3 months) use of smoking cessation medications or nicotine replacement therapy (NRT);
4. A baseline carbon monoxide (CO) reading less than 8ppm.

Alcohol/Drugs:

1. Diagnosis or treatment for alcohol or drug abuse in the past two years as reported during phone screen (e.g., alcohol, opioids, cocaine, or stimulants);

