2. Current alcohol consumption that exceeds 25 standard drinks/week;
3. Positive breath alcohol concentration test (BrAC greater than or equal to 0.01) at intake;
 - a. Participants testing positive for breath alcohol with a reading equal to or greater than .08 (the legal driving limit) or who are visibly impaired will be instructed not to drive themselves home after the appointment. If a participant needs to use a phone to call for a safe ride home, an office telephone will be made available to the participant.
4. A positive urine drug screen for cocaine, opiates, PCP, benzodiazepines, methadone, MDMA, amphetamine, methamphetamine, tri-cyclic antidepressants and/or barbiturates at any session;

Medication:

Current use or recent discontinuation (within the past 30 days at the time of Intake) of:

1. Smoking cessation medication (e.g., Zyban, Wellbutrin, Wellbutrin SR, Chantix, NRT);
2. Anti-psychotic medications;
3. Anti-depressants (tricyclics, SSRI's, selective and nonselective MAOIs, Wellbutrin/Zyban);
4. Anti-anxiety agents;
5. Anti-obsessive agents;
6. Anti-panic agents;

7. Prescription (e.g., Provigil, Ritalin) or over-the-counter stimulants;
8. Prescription sleep aids (e.g., Ambien, Lunesta) if used more than 2x/week. If participants report use less than twice a week, they will just be asked to refrain from use during imaging portion of the study.
9. Any medication that could compromise participant safety as determined by the Principal Investigator and/or Study Physician;

Daily use of:

10. Opiate-containing medications for chronic pain.

Medical/Neuropsychiatric:

1. Women who are pregnant, planning a pregnancy, and/or breast feeding. All female subjects of childbearing potential will undergo a urine pregnancy test at Intake and both fMRI scan visits (3 urine pregnancy tests in total).
2. History of epilepsy or a seizure disorder;
3. History of stroke;
4. Self-reported brain or spinal tumor;
5. Self-reported history or current diagnosis of psychosis, bipolar disorder, schizophrenia, current major depression (subjects with a history of major depression but in remission for past 6 months are eligible), or any Axis 1 disorder;
6. Self-reported history or current diagnosis of Attention-Deficit Hyperactivity Disorder (ADHD).

fMRI-Related:

1. Self-reported history of head trauma: loss of consciousness for 3 minutes or longer, hospitalization as a result of head injury, cognitive impairment following head injury

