2. Self-reported brain (or CNS) or spinal tumor;
3. Self-reported use of pacemakers, certain metallic implants, or presence of metal in the eye as contraindicated for fMRI;
4. Self-reported history of claustrophobia;
5. Being left-handed;
6. Color blindness;
7. Weight greater than 275 lbs at intake;
8. Self-reported history of gunshot wounds;
9. Any impairment preventing participants from using the response pad necessary for the cognitive testing;
10. Circumstances or conditions that may interfere with magnetic resonance imaging (MRI).

General Exclusion:

1. Any medical condition, illness, disorder, or concomitant medication that could compromise participant safety or treatment, as determined by the Principal Investigator;
2. Low or borderline intellectual functioning – determined by a score of less than 85 on the Shipley Institute of Living Scale (SILS) (administered at Intake Visit). The SILS correlates with the Wechsler Adult Intelligence Scale-Revised (WAIS-R) Estimated IQ Test;
3. Enrollment or plans to enroll in another research study;
4. Inability to provide informed consent or complete any of the study tasks as determined by the Principal Investigator.

5. Vulnerable Populations

Children (under age 18), pregnant women or prisoners are not included in this research study.

6. *Populations vulnerable to undue influence or coercion*

Educationally or economically disadvantaged persons are included but not solely targeted for recruitment. Cognitively impaired persons are not included in the current study. Because of our recruitment efforts for this study, it is possible that University of Pennsylvania employees and students may be invited to participate. Status of participation in the current study will be independent of the participant's work or school activities.

7. *Subject Recruitment*

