Key Exclusionary Criteria; Alcohol/Drugs). Participants who test positive for any exclusionary medications or recreational drugs will be deemed ineligible;

3. Self-administer a CLIA-waived urine pregnancy test (female participants of childbearing potential only). Participants who believe that they may be pregnant are instructed to discontinue participation at this time;
4. Perform a BrAC assessment to control for alcohol consumption. Participants with a BrAC greater than or equal to 0.01 at Intake Visit will be ineligible;
5. Participants will be asked to perform a CO breath assessment to verify smoking status. Participants with CO readings less than 8 parts per million (ppm) will be ineligible.
6. Complete a brief medical history form with a trained staff member; for female participants, this form will include brief questions regarding menstrual cycle phase and hormonal contraception use.
7. Complete Shipley Institute of Living Scale (SILS) IQ test. Participants earning less than an estimated WAIS-R IQ score of 85 will be ineligible;
8. Complete demographics and smoking history (smoking rate, nicotine dependence, age at smoking initiation, childhood adverse events) and paper and pencil questionnaires (craving, withdrawal, mood, intention to quit smoking, impulsivity and anxiety);
9. Complete the Magnet Safety Form and Emergency Contact Form as required for scheduling fMRI scans;
10. Provide a saliva sample for baseline Nicotine Metabolite Ratio (NMR) assessment.

Participants will be asked to refrain from using any study prohibited drugs (note – participants are allowed to take prescription medicines not in the exclusion list) throughout their participation in the study.

fMRI Scanning Sessions (Weeks 1 & 2). All participants will have two imaging sessions prior to their target quit date (week 1 & week 2). Both scan sessions will be identical except for the participant smoking status. One scan will be after 24 hours of abstinence (acceptable range = 18-30 hours) and the other after smoking as usual. Visits on scanning days can be scheduled at any time of day, as long as the second scan is within a 3-hour window +/- of the first scan. Including the 1hr fMRI scan, these visits are expected to be ~4hrs in duration.

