24-hour Abstinent Scan: Participants will be contacted ~48 hours prior to the scheduled abstinent scan to remind them not to smoke for 24 hours prior to the scan visit. The timing of cessation for each subject will be based on the scheduled scan time (e.g., if the scan is at 10 a.m., they will refrain from smoking after 10 a.m. on the prior day).

Smoking as Usual Scan: Participants will be contacted ~48 hours prior to the scheduled smoking-as-usual scan and instructed to smoke as usual prior to their visit. To standardize smoking across participants, they will smoke a cigarette about 30-40 minutes prior to the fMRI scan.

At both scans participants will:

1. Complete a urine drug screen (at least 30ml [two tablespoons] of urine). The urine drug screen will assess the use of any study-prohibited medications/recreational drugs (See Key Exclusionary Criteria; Alcohol/Drugs). Participants who test positive for any exclusionary medications or recreational drugs will be deemed ineligible.
2. Complete a urine pregnancy test (female participants of childbearing potential only). Self-administer a CLIA-waived urine pregnancy test (female participants only). Participants who believe that they may be pregnant are instructed to discontinue participation at this time;

3. Complete a CO breath assessment. This CO screen is to confirm that participants are in the appropriate nicotine state for that session.
 - a. For the abstinent scan, participant's CO reading should be less than 8ppm or a 50% reduction from the baseline CO level (taken at the Intake Visit) to confirm that participants are compliant with the smoking requirements for this session.
 - b. For the smoking session, participant's CO reading should be greater than or equal to 8ppm to confirm that participants are compliant with the smoking requirements for this session. A CO reading as low as 7ppm will be acceptable if there is a viable explanation (for example, the participant has a cold that day). If the CO readings do not meet the ranges provided here, they will be excluded from the study and forfeit future compensation.
4. Complete a BrAC assessment to control for alcohol consumption. Participants with a BrAC greater than or equal to 0.01 at either scan will be ineligible;

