Urine Pregnancy Test: At the Intake and both fMRI scanning sessions female participants of childbearing potential will be supplied with a simple, CLIA-waived urine pregnancy screen and informed that pregnant women are not advised to participate in this research study. Participants will then be instructed to administer the pregnancy test independently and will inform study staff

if they would like to continue participation after they have administered the pregnancy screen. Participants will be informed that there is no penalty for discontinuing participation at this point in the visit and that they will still be provided with their preferred travel coverage.

ETOH History: ETOH history will be administered at the Intake Visit and will ask subjects about their alcohol consumption over the past 7 days.

Breath Alcohol Concentration: The BrAC assessment will be administered at all study visits. The breath alcohol monitor is a handheld device that uses a disposable mouthpiece and reports the concentration of alcohol in exhaled breath. Any reading > 0.000 indicates alcohol consumption within the last 14 hours. Participants with a BrAC greater than or equal to 0.01 at the Intake Visit will be ineligible. Participants who have a BrAC reading greater than or equal to 0.01 at Intake or either scanning visit may be ineligible to continue with the visit and will only be rescheduled/allowed to proceed with the study at the discretion of the Principal Investigator.

Smoking Behavior: At the intake visit, participants will complete the 6-item Fagerstrom Test for Nicotine Dependence (FTND) [43] and a smoking history assessment which includes age at first cigarette, age at regular (daily) smoking, and current smoking rate. Number of cigarettes smoked in past 24 hours and time of last cigarette will be recorded at each visit.

Medical: Height and weight will be measured and recorded. All participants will complete a medical history form with a trained staff member to review for all contraindications listed previously.

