The greatest risk with MRI is a metallic object flying through the air toward the magnet and hitting the participant. To reduce this risk we require that all people involved with the study remove all metal from their clothing and all metal objects from their pockets. No metal objects are allowed in the magnet room at any time. In addition, once the participant is in the magnet, the door to the room will be closed so that no one inadvertently walks into the magnetic field. Although there are no known risks of MRI on pregnant women or a fetus, there is a possibility of yet undiscovered pregnancy related risks. Since there is no direct benefit from participating in this protocol for a pregnant woman, women of child bearing potential will be supplied with a simple, CLIA-waived urine pregnancy screen to self-administer at each scan visit, and will be advised that we recommend that pregnant women do not participate in the study. They will then be instructed to administer the pregnancy test independently and will inform study staff if they would like to continue participation after they have administered the pregnancy screen. Participants will be informed that there is no penalty for discontinuing participation at this point in the visit and that they will still be provided with their preferred travel coverage.

There is no known health risk associated with exposure to magnetic fields during an MRI. There are minimal risks from the loud noise associated with the MRI scanner and from the discomfort of lying on a hard surface. Participants will be provided with protective earplugs as necessary and every attempt will be made to ensure comfort with blankets, etc. during the scan.

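### Pregnancy is a categorical exclusion, but the sections describing the pregnancy test disagree and none ties a positive result to ineligibility

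*Combined protocol and SAP*

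**What the plan says.** Under Key Exclusion Criteria, the Medical/Neuropsychiatric list opens with "Women who are pregnant, planning a pregnancy, and/or breast feeding". The lead-in to the exclusion lists gives each item force throughout the study: "Subjects who present and/or self-report with the following criteria at any point during study participation will not be eligible". Women of childbearing potential "will undergo a urine pregnancy test at Intake and both fMRI scan visits (3 urine pregnancy tests in total"). Vulnerable Populations adds: "Children (under age 18), pregnant women or prisoners are not included in this research study".

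Study Procedures describes the test at Intake as "Self-administer a CLIA-waived urine pregnancy test (female participants of childbearing potential only") and has a matching item for the scan visits. Both items carry the same instruction: "Participants who believe that they may be pregnant are instructed to discontinue participation at this time".

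Measures (Urine Pregnancy Test) and Potential Study Risks (fMRI) describe the step differently. Women are told that taking part while pregnant is discouraged. They carry out the test on their own and then let staff know "if they would like to continue participation after they have administered the pregnancy screen". Both sections add that stopping carries no penalty and that travel is still covered. The risk section says that MRI has no known risks for pregnant women or a fetus, but that "there is a possibility of yet undiscovered pregnancy related risks". Together with the absence of direct benefit to a pregnant woman, that is its reason for testing.

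**The concern.** The protocol tells the IRB that no pregnant women take part, and it introduces a test to support that statement. Two of the sections that describe the test then leave the next step to the participant's stated wish. Staff following those sections as written could scan a woman whose test is positive, while staff following the exclusion list could not.

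What is at stake is a safety property that the protocol states but its procedure does not assure, at the visits where the precaution is meant to apply. Staff also lack a single instruction for an event that the protocol itself anticipates.

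**Working it through.** No power, alpha or event figure is involved, so the check is a comparison of the sections.

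| Section | Status given to pregnancy | What triggers action | Who acts |
|---|---|---|---|
| Key Exclusion Criteria; Vulnerable Populations | Ineligible at any point; not included | Presenting with, or self-reporting, the condition | Not stated |
| Study Procedures: Intake and fMRI Scanning Sessions | Instructed to stop | The participant's belief that she may be pregnant | The participant, on instruction |
| Measures: Urine Pregnancy Test | Advised against taking part | The participant's stated wish | The participant |
| Potential Study Risks: fMRI | Recommended not to take part | The participant's stated wish | The participant |
| For contrast, urine drug screen (Intake, scan visits, Measures) | Ineligible | A positive result | The study; Measures says the result is not shared with the participant |

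1. The first two rows are compatible. An instruction to stop is one way of carrying out an exclusion, although its trigger is belief and not the test result.
2. The first row and the third and fourth rows part company in one case: a woman with a positive test who tells staff she wishes to continue. The first row makes her ineligible. The third and fourth rows give staff no stated ground to stop her, because the only information they route to staff is her wish.
3. No other section settles that case. Tissue Specimens says urine is needed at Intake and at every scan session for drug and pregnancy screening, but not who reads the pregnancy test. No sentence in the supplied text links a positive pregnancy test to ineligibility. The drug screen has that sentence in three places, so the protocol does state such rules elsewhere.
4. The schedule is consistent: 1 test at Intake + 2 at the scan visits = 3, which agrees with Key Exclusion Criteria and with Table 2. The inconsistency concerns what follows the test, not when it is done.
5. The number of women of childbearing potential is not given, so the number of affected tests cannot be calculated.

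**The case against.** The best defence is that the exclusion has other supports. The lead-in to the exclusion lists removes anyone who reports a pregnancy at any time. A trained staff member completes the medical history at Intake, which for women includes questions on menstrual cycle phase and hormonal contraception. The investigator may exclude for any condition that could compromise safety. The procedures do instruct a woman who thinks she may be pregnant to stop. The protocol also relies on self-report for several MRI contraindications, such as pacemakers and metallic implants, and self-testing may be a deliberate privacy or regulatory choice. Finally, neither Measures nor the risk section says outright that a woman with a positive test may be scanned.

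Much of this stands, and it rules out a stronger reading that a reader might infer: that participants read their own results, that staff never see them, and that the exclusion is therefore unenforceable. The documents say that the test is self-administered and done independently. They do not say who reads it, so a participant-only reading is an inference. Staff can act on a reported pregnancy. Nor do the documents support reading this as exposure to a known hazard, since the risk section says no MRI risk in pregnancy is known.

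The defence does not remove the conflict. Each support depends on disclosure, belief or discretion, and none says what follows a positive test. A privacy reason would explain the self-testing but would not reconcile it with a categorical exclusion.

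**Conclusion.** The inconsistency is real and should be corrected. Pregnancy is excluded without qualification in one place, met with an instruction to stop in another, and left to advice and the participant's wish in two more. As described, the test cannot be used by staff to confirm the exclusion, and its result has no stated consequence.

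The size is modest. It concerns eligibility and safety wording at up to three tests per woman of childbearing potential and has no bearing on the sample size, power or the time-to-relapse analysis. The conclusion rests on the supplied text. Consent pages were not available, so a rule stated there could not be checked; even so, the protocol sections would still need to agree with one another.

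**What to change.** Reconcile Key Exclusion Criteria, Vulnerable Populations, the Intake and scan-visit procedures, Measures (Urine Pregnancy Test) and Potential Study Risks (fMRI). One consistent rule should state what follows a positive test and who acts on it, including whether staff see and record the result. If the participant's choice is intended to govern, correct the statements that pregnant women are excluded and not included. Which rule stands is for the study physician and the IRB; none is proposed here.

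The cost is a protocol wording amendment, with a check that the consent form matches. No change to the analysis plan is needed.

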The target quit date session will be scheduled to occur up to 2 weeks following the pre-quit session. Prior to the booster counseling sessions, self-reported smoking will be assessed (time line follow back, CO, saliva cotinine and urinary cotinine); we will also administer self-report questionnaires (e.g., smoking urges, withdrawal and mood). Days to relapse (primary outcome) will be defined as number of consecutive days prior to 7-day relapse (7 consecutive days of smoking). Participants will then meet with a smoking cessation counselor for a 15 minute booster counseling session. Participants will receive small monetary incentives for each week of biochemically confirmed abstinence based on CO level (<=5ppm) and/or urine cotinine assessment (NicAlert, Nymox Pharmaceutical Corporation, Hasbrouck Heights, NJ) that also indicates no smoking during the past 7 days (\$75/week). Participants will be paid in cash after abstinence has been verified (and will not be paid for a missed visit). There is a \$50 bonus for participants who have attended at least 4 of the 5 in-person monitoring visits. Telephone assessments and counseling may be provided if participants miss a visit, at the discretion of the PI.

6 Month Follow-up (~Week 28). Participants who are biochemically verified to be quit at MV5 will be contacted 24 weeks post TQD by telephone to complete a brief survey of their smoking practices using the timeline follow-back assessment. Those who report not smoking a cigarette for at least the past 7 days prior to completing the survey will be asked to come to the Center for biochemical verification of smoking status by providing CO, saliva cotinine and a urine cotinine sample.

12 Month Follow-up (~Week 52). Participants who completed all visits up to and including the Pre-Quit visit will be contacted 48 weeks post TQD by telephone to complete a brief survey of their smoking practices and eating behavior. All measures collected at the 6 Month Follow-up will be collected with the addition two questions about readiness and intention to quit smoking (if applicable).

Table 2. Measures and Time Points

Activity	Phone Screen	Intake	fMRI Scans	Pre-Quit	TQD	MV 1-5	Follow-up	12-month Follow-up
Weeks	-1	0	1, 2	3	4	5, 6, 7, 8	28	52
Demographics		X						
Urine drug screen		X	X					
Urine pregnancy screen		X	X					
ETOH history/BrAC		X						
Height		X						
Weight		X						
Smoking behavior (FTND)		X						
Medical history form		X						

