Salivary testosterone: Salivary testosterone will be used to control for between-session differences that may occur due to change in testosterone levels in male and female participants. Testosterone (pg/ml) will be collected at the start of the scan session. Approximately 2 ml of saliva will be collected using a passive drool method and saliva collection aid (Salivette LLC, State College, PA, USA). The saliva will be stored in plastic vials at –20°C. Saliva samples will be assayed using testosterone EIA kits (Salimetrics LLC, State Collect, PA, USA). Salivary testosterone is highly correlated with plasma testosterone [55].

fMRI Measures: See fMRI Scanning Sessions above.

Primary Outcomes (Main Study): Multiple measures of abstinence will be measured for this study. The primary outcome will be the number of days to relapse following the target quit date. Relapse will be confirmed using a conventional SRNT guideline criterion of either a positive biochemical verification of smoking [3, 56] or 7 consecutive days of smoking based on self-report (it is very unlikely that a subject would meet the latter criterion without also meeting the former, given the long half-life of cotinine). The days to relapse will be based upon time from target quit date to the first day of the relapse period. Self-reported daily smoking data will be collected using a validated timeline follow-back method [57]. Self-reported abstinence will be biochemically verified on a weekly basis using urine cotinine (<100ng/ml) [56] and a CO reading

of ≤5PPM. Drop-outs will be considered relapsers following the last date of abstinence data provided [7, 58]. Secondary outcomes will include days to first “slip”, and cross-sectional measures of 7-day and 30-day point prevalence (biochemically verified weekly with cotinine, which provides an assessment of smoking in the last 7 days).

Carbon Monoxide (CO): The CO monitor is a handheld device that uses a disposable mouthpiece, reports CO in parts per million (ppm), and takes about 5 minutes to administer. Carbon monoxide measurements will be collected from smokers at each visit as a biochemical verification of smoking exposure.

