Urine Cotinine: Smoking status will be assessed with NicAlert™ urine dipsticks from Nymox Pharmaceutical Corporation. A midstream urine sample of approximately 25mL will be used to test for the presence of cotinine. Results will appear in one of seven category levels of usage. Level 0 indicates no detectable tobacco use; levels 1-2 indicate presence of cotinine, but as a non-user, and levels 3-6 indicate cotinine consistent with tobacco use. Participants with results in levels 3-6 will be considered smokers. Urine cotinine will be assessed at all Monitoring Visits 2-5, if participant has reported weekly abstinence.

Saliva Cotinine: Saliva cotinine will be collected to biochemically verify smoking status. Saliva samples will be collected at monitoring visits 2-5 from participants who report smoking abstinence and have a CO value of less than or equal to 5ppm.

Primary Outcomes (Recruitment & Retention Pilot Study):

Meeting Eligibility Criteria: The primary outcome is the percentage of subjects who meet final eligibility criteria (i.e., enrollment). We chose this as the outcome based on our data suggesting that subjects who meet these criteria are highly likely to reach ITT status.

Secondary Subjective Outcomes (Main Study):

Mood: Positive and Negative Affect: The Positive and Negative Affect Schedule (PANAS) [59], a 20-item Likert-format self-report measure, will be used to assess Positive Affect (PA; 10 items, e.g., enthusiastic, strong) and Negative Affect (NA; 10 items, e.g., distressed, upset), two dominant and generally orthogonal dimensions of affect.

Nicotine Withdrawal: The Revised Minnesota Nicotine Withdrawal Scale (MNWS-R) [60] is a fifteen-item self-report measure where participants rate their feelings of withdrawal on a scale of 0 (none) to 4 (severe). This measure will be administered at all study visits.

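### Cotinine is taken only from participants who report abstinence, yet a positive test alone is relapse, so smoking that visit CO misses is a primary event if denied and not if admitted

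*Combined protocol and SAP*

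**What the plan says.** Four places bear on the primary event.

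- **Measures, Primary Outcomes (Main Study).** Relapse is "either a positive biochemical verification of smoking [3, 56] or 7 consecutive days of smoking based on self-report". The first limb is sufficient by itself. The section adds that "it is very unlikely that a subject would meet the latter criterion without also meeting the former, given the long half-life of cotinine". Days to first slip is listed separately, as a secondary outcome.
- **Measures, Urine Cotinine and Saliva Cotinine.** "Urine cotinine will be assessed at all Monitoring Visits 2-5, if participant has reported weekly abstinence". For saliva, "Saliva samples will be collected at monitoring visits 2-5 from participants who report smoking abstinence and have a CO value" of 5 ppm or less. CO itself is measured at every visit, whatever the participant reports.
- **Study Procedures, Monitoring Visits.** Before booster counseling, "self-reported smoking will be assessed (time line follow back, CO, saliva cotinine and urinary cotinine") with no condition attached. Days to relapse is the "number of consecutive days prior to 7-day relapse (7 consecutive days of smoking"), with no biochemical limb. Table 2 also marks both cotinine tests for the monitoring visits without a condition.
- **Study Procedures, 6 Month Follow-up.** "Those who report not smoking a cigarette for at least the past 7 days prior to completing the survey" are the ones asked to come in for verification, so the condition on self-report recurs there.

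**The concern.** Testing only those who claim abstinence is natural when the endpoint is quit or not quit, because admitted smoking already counts as failure. Here it does not: admitted smoking short of 7 consecutive days is not relapse. Joining that threshold to a biochemical limb that only self-declared abstainers can meet through cotinine makes the event depend on reporting as well as on smoking.

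The protocol pays $75 per week for confirmed abstinence, which gives some participants a reason to deny a slip. A denied slip that is detected moves from the secondary outcome (first slip) into the primary outcome. It also has no self-reported start, so the instruction to count to the first day of the relapse period cannot be followed without a further rule. At stake is what the Aim 1 Cox models estimate: the hazard of relapse, or a mixture of relapse and detected denial.

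**Working it through.** **1. The rules side by side.** Take a participant who smoked in the week before one of MV2–MV5 without any run of 7 consecutive smoking days.

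| | Smoking denied | Same smoking admitted |
|---|---|---|
| Urine cotinine | taken | not taken |
| Saliva cotinine | taken if CO ≤5 ppm | not taken |
| 7-day self-report limb | not met | not met |
| Primary Outcomes definition, CO ≤5 ppm, cotinine would be positive | event | no event |
| Primary Outcomes definition, CO >5 ppm | event | not stated |
| Visit-text definition (7 consecutive days only) | no event | no event |

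The asymmetry is in the fourth row. It follows from the text alone.

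**2. The plan's power figure.** This is the only stated number for the primary analysis, and the point does not depend on it. Inputs: N = 200, effect size 0.25, alpha 0.0085, taken as two-sided.

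Power = Φ(0.25 × √200 − z(1 − 0.0085/2)) = Φ(3.536 − 2.632) = 81.7%, or 80.9% with a noncentral t. The stated 80% reproduces.

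For HR 1.32 per SD (SD of 1 assumed), the events needed are (2.632 + 0.842)² / (ln 1.32)² = 157, which is 78% of 200. The documents give no expected event count. If 65% relapsed (130 events), power would be Φ(0.2776 × √130 − 2.632) = about 70%.

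**3. Events per 100 participants with a slip, no 7-day run, and CO missed** (assumed rates). Events under the restricted rule = 100 × P(deny) × P(detect). Denial of 10–50% and detection of 50–100% give 100 × 0.1 × 0.5 = 5 up to 100 × 0.5 × 1.0 = 50. Testing everyone gives 50–100. The 7-day-only definition gives 0.

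**4. Simulation of dilution** (assumed rates, 1,500 runs per setting). N = 200, HR 1.32 per SD for 7-day relapse, 65% relapsed by day 28, follow-up ending at day 28. Slips occur in 10–20% of still-abstinent participants per week, and 25–50% of slips are denied and detected. CO is taken to miss the slips.

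- About 10–38 participants have an event at a visit only because they denied a slip. Another 18–48 had slips that were not scored.
- Slips unrelated to the ROI: fitted HR 1.23–1.30; power falls from 66–69% to 45–62%.
- Slips with HR 1.16: a loss of about 1–7 power points.
- Slips sharing HR 1.32: HR little changed (about 1.30–1.32); power rises from 66–70% to 70–75%, because events are added.

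**5. Simulation of bias** (assumed rates, 3,000 runs). N = 200, 30 days, 60% relapse, 60% slip, 80% detection, 30% denial unless stated. Predictor unrelated to slips and relapse; nominal level 0.85%.

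| Denial odds ratio per SD | Restricted rule: HR, type I error | Everyone tested: HR, type I error |
|---|---|---|
| 1 | 1.00, 0.8% | 1.00, 0.7% |
| 1.5 | 1.05, 1.5% | 1.00, 0.6% |
| 2 | 1.08, 3.0% | 1.00, 0.7% |

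At an odds ratio of 1.5, 10% baseline denial gives HR 1.02 with type I error of 0.8%; 50% gives HR 1.05 with 2.3%. With a true HR of 1.32 for both relapse and slips and a denial odds ratio of 0.67, the fitted HR is about 1.25.

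**The case against.** Much of the case on the other side limits the reach of the point without removing it.

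- **CO is taken from everyone.** An admitted smoker with CO above 5 ppm could be read as meeting the biochemical limb, so a reader who infers that admitted non-daily smoking never counts goes too far. The plan does not say whether such a reading counts. It does expect cotinine to add to CO: saliva is taken precisely when CO is low, and cotinine is described as covering the last 7 days.
- **One cigarette need not turn the test positive.** A positive dipstick is level 3–6, and the documents give no sensitivity for a single cigarette some days earlier. The point covers only smoking that cotinine would detect.
- **Dilution is not a given.** One might infer that the rule weakens the ROI effect and costs a definite amount of power. That requires slips to be unrelated to the ROI, whereas the Background argues that altered brain responses weaken resistance to urges. If slips share the effect, power does not fall.
- **The remark that the two limbs nearly always coincide cannot be checked with cotinine,** because self-reported smokers are not given the test. One might infer that this undermines the outcome. It does not: participants with 7 reported smoking days are already events, so no classification changes, and deleting the remark would be editorial.
- **Reconciling the definitions may dissolve the problem.** Under the visit-text definition neither slip is an event. True, but the plan has not chosen, and the definition in its outcome section produces the asymmetry.

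**Conclusion.** The point holds in a limited form. As the outcome and cotinine sections are written, smoking short of 7 consecutive days that cotinine would detect and visit CO would miss is a primary event when denied and not when admitted. This applies at MV2–MV5, and the same condition recurs at the 6-month check. It conflicts with the monitoring-visit text and Table 2 on who is tested, and with the visit text on what relapse is.

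The size cannot be derived from the documents; every rate in the simulations is an assumption. The direction is conditional: dilution if slips are unrelated to the ROI, little change if they share its effect, and bias in the hazard ratio with type I error above 0.85% if denial is related to the ROI and common enough. A claim that the study loses a stated amount of power for this reason is not supported. The passages should still be reconciled, because the primary event is ambiguous and the repair is cheap.

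**What to change.** Reconcile the Primary Outcomes, Urine Cotinine, Saliva Cotinine and monitoring-visit text and Table 2 to one event rule that does not depend on whether smoking is admitted. Two routes are available.

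1. Run the MV2–MV5 urine dipstick on every attendee regardless of self-report, and apply the same rule to every positive cotinine or CO result. Cost: some additional dipsticks, on samples that the visit text and Table 2 already list.
2. Take 7 consecutive smoking days as the event and score an isolated positive test as a slip, which is already a secondary outcome. Cost: wording and derivation only, but concealed relapse may be missed or dated late, so the plan must say how repeated positives in someone who keeps denying are scored.

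Under either route, state how an event is dated when smoking is denied, how an unconfirmed positive at MV5 is scored (no weekly test follows it), and whether CO above 5 ppm in an admitted smoker counts. Apply the same rule to the 6-month check, and report the other definition as a sensitivity analysis.

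Keeping the self-report condition and merely asking for a second positive test is not enough. Someone who denies non-daily smoking every week would be tested twice and relapsed, while someone who admits the same pattern would not be tested at all.
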